Appendix R. Participant Track Books

Intervention

SUNDAY

How many cups of vegetables did you eat?

- 0
- 1/2 cup
- 1 cup
- 1 1/2 cups
- 2 cups
- 2 1/2 cups
- 3 cups
- OTHER: _____

How many cups of fruit did you eat?

- 0
- 1/2 cup
- 1 cup
- 1 1/2 cups
- 2 cups
- OTHER: _____

Dates This Week: ____/____ to ____/____

TRACK BOOK

How many fruits and vegetables did you eat this week? _____

Total cups of vegetables eaten this week: _____

Did you eat at least 2.5 cups of vegetables this week? YES NO

Total cups of fruit eaten this week: _____

Did you eat at least 1.5 cups of FRUIT this week? YES NO

If you have any questions,
please call [contact], [name].

If you need to access the
POW-R automated phone system,
call [name].

MONDAY

How many cups of vegetables did you eat?

- 0
- $\frac{1}{2}$ cup
- 1 cup
- $1\frac{1}{2}$ cups
- 2 cups
- $2\frac{1}{2}$ cups
- 3 cups
- OTHER: _____

How many cups of fruit did you eat?

- 0
- $\frac{1}{2}$ cup
- 1 cup
- $1\frac{1}{2}$ cups
- 2 cups
- OTHER: _____

SATURDAY

How many cups of vegetables did you eat?

- 0
- $\frac{1}{2}$ cup
- 1 cup
- $1\frac{1}{2}$ cups
- 2 cups
- $2\frac{1}{2}$ cups
- 3 cups
- OTHER: _____

How many cups of fruit did you eat?

- 0
- $\frac{1}{2}$ cup
- 1 cup
- $1\frac{1}{2}$ cups
- 2 cups
- OTHER: _____

FRIDAY

How many cups of vegetables did you eat?

- 0
- $\frac{1}{2}$ cup
- 1 cup
- $1\frac{1}{2}$ cups
- 2 cups
- $2\frac{1}{2}$ cups
- 3 cups
- OTHER: _____

How many cups of fruit did you eat?

- 0
- $\frac{1}{2}$ cup
- 1 cup
- $1\frac{1}{2}$ cups
- 2 cups
- OTHER: _____

TUESDAY

How many cups of vegetables did you eat?

- 0
- $\frac{1}{2}$ cup
- 1 cup
- $1\frac{1}{2}$ cups
- 2 cups
- $2\frac{1}{2}$ cups
- 3 cups
- OTHER: _____

How many cups of fruit did you eat?

- 0
- $\frac{1}{2}$ cup
- 1 cup
- $1\frac{1}{2}$ cups
- 2 cups
- OTHER: _____

WEDNESDAY

How many cups of vegetables did you eat?

- 0
- ½ cup
- 1 cup
- 1 ½ cups
- 2 cups
- 2 ½ cups
- 3 cups
- OTHER: _____

How many cups of fruit did you eat?

- 0
- ½ cup
- 1 cup
- 1 ½ cups
- 2 cups
- OTHER: _____

THURSDAY

How many cups of vegetables did you eat?

- 0
- ½ cup
- 1 cup
- 1 ½ cups
- 2 cups
- 2 ½ cups
- 3 cups
- OTHER: _____

How many cups of fruit did you eat?

- 0
- ½ cup
- 1 cup
- 1 ½ cups
- 2 cups
- OTHER: _____

Control

SUNDAY

How many cups of vegetables did you eat?

- 0
- ½ cup
- 1 cup
- 1 ½ cups
- 2 cups
- 2 ½ cups
- 3 cups
- OTHER: _____

How many cups of fruit did you eat?

- 0
- ½ cup
- 1 cup
- 1 ½ cups
- 2 cups
- OTHER: _____

Dates This Week: ____/____ to ____/____

TRACK BOOK

How many fruits and vegetables did you eat this week? _____

Total cups of vegetables eaten this week: _____

Did you eat at least 2.5 cups of vegetables this week? YES NO

Total cups of fruit eaten this week: _____

Did you eat at least 1.5 cups of FRUIT this week? YES NO

If you have any questions, please call [contact], [name].

If you need to access the POW-R automated phone system, call [name].

MONDAY

How many cups of vegetables did you eat?

- 0
- ½ cup
- 1 cup
- 1 ½ cups
- 2 cups
- 2 ½ cups
- 3 cups
- OTHER: _____

How many cups of fruit did you eat?

- 0
- ½ cup
- 1 cup
- 1 ½ cups
- 2 cups
- OTHER: _____

SATURDAY

How many cups of vegetables did you eat?

- 0
- ½ cup
- 1 cup
- 1 ½ cups
- 2 cups
- 2 ½ cups
- 3 cups
- OTHER: _____

How many cups of fruit did you eat?

- 0
- ½ cup
- 1 cup
- 1 ½ cups
- 2 cups
- OTHER: _____

FRIDAY

How many cups of vegetables did you eat?

- 0
- $\frac{1}{2}$ cup
- 1 cup
- $1\frac{1}{2}$ cups
- 2 cups
- $2\frac{1}{2}$ cups
- 3 cups
- OTHER: _____

How many cups of fruit did you eat?

- 0
- $\frac{1}{2}$ cup
- 1 cup
- $1\frac{1}{2}$ cups
- 2 cups
- OTHER: _____

TUESDAY

How many cups of vegetables did you eat?

- 0
- $\frac{1}{2}$ cup
- 1 cup
- $1\frac{1}{2}$ cups
- 2 cups
- $2\frac{1}{2}$ cups
- 3 cups
- OTHER: _____

How many cups of fruit did you eat?

- 0
- $\frac{1}{2}$ cup
- 1 cup
- $1\frac{1}{2}$ cups
- 2 cups
- OTHER: _____

WEDNESDAY

How many cups of vegetables did you eat?

- 0
- ½ cup
- 1 cup
- 1 ½ cups
- 2 cups
- 2 ½ cups
- 3 cups
- OTHER: _____

How many cups of fruit did you eat?

- 0
- ½ cup
- 1 cup
- 1 ½ cups
- 2 cups
- OTHER: _____

THURSDAY

How many cups of vegetables did you eat?

- 0
- ½ cup
- 1 cup
- 1 ½ cups
- 2 cups
- 2 ½ cups
- 3 cups
- OTHER: _____

How many cups of fruit did you eat?

- 0
- ½ cup
- 1 cup
- 1 ½ cups
- 2 cups
- OTHER: _____

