Let's now talk about some obstacles that could make it harder for you to complete your plan. What are one or two obstacles that could make it harder for you to eat your power vegetables every day?

Obstacle 1

Obstacle 2

What are some strategies you could use to help overcome the obstacles you listed?

Obstacle 1, Strategies (2-4)

Obstacle 2, Strategies (2-4)

My plan this week to eat more power vegetables

Now let's make a plan to eat more power vegetables this week. The next time you or someone else goes to the grocery store, which power vegetables will you buy with medium to high isothiocyanates (page 7)?

Power vegetables to buy

The next time you eat power vegetables, how will you make them? Remember that when you cook the power vegetable, to cook it for less than 10 minutes.

Raw, microwave, sauté/stir-fry, steam

 Part G: Go over POW-R Track Book

One of the things you received in the packet we mailed to you is a POW-R Book. Please have your POW-R Book ready to review. In this book, I am asking that you keep track of how many power vegetables you eat every day, and each week. Science shows that keeping track of what you eat is a powerful way to change your habits. Keeping track of how many power vegetables you eat will help you eat more power vegetables. Let's go over all of the parts of the POW-R Book.

Check box when section is covered			
1. 1 POW-R book for each week; 24 sent to you—1 is for practice to use now. We are asking you to keep track of how many power vegetables you eat every week for the entire program.	3. 7 days in one POW-R book	5. Each day you say whether you ate at least 1 power vegetable cup where you prepared it in a POW-R Health Preferred way (explain what this is)	7. On the back is the phone number of the person from our team that you can call if you have any questions.
2. Cover page—write down dates of the week you are keeping track	4. Each day you write down how many cups of power vegetables you had at dinner or after dinner . Only write down those power vegetables you ate at dinner or after dinner (have them open book)	6. On the first page, is where you will write down the total number of power vegetables you ate at dinner or after dinner for that week. After our phone call, you will receive automated messages and will be asked to enter the number of cups of power vegetables you ate for the week.	8. Any questions?

Let's practice using the POW-R Track Book.

 Practice using POW-R Track Book

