Take a POW-R Track Book. Can you think back this past week of any power vegetables you ate at dinner or after dinner? If you did not eat any power vegetables, how about any type of vegetable? Let's go through each day.

Monday	Tuesday	Wed
Thursday	Friday	Sat
		Sunday

Not let's add how many cups you ate that week

Total	Correct
No	Yes

CORRECT: Yes, that's right- good job!

INCORRECT: Ok, so the correct total is X. Let's try that again to make sure you can use the POW-R Book correctly.

Feel free to use a calculator if that would make things easier.

□ Part H: Going over magazine components: Teach Back Opportunity #3

Only ask questions that were answered incorrectly in Part E. SKIP if all questions were answered correctly in Part D or E.

Is this Part applicable?

No Yes

Before we end the call, I just want to re-ask you the questions about the key points from the magazine that you were not able to recall last time

TB1.3 What is a power vegetable?

Correct: A cruciferous vegetable

Correct

No Yes

CORRECT: Yes, that's right! A power vegetable is a certain type of vegetable called cruciferous vegetables.

INCORRECT: Power vegetables are cruciferous vegetables.

TB2.3 Please give me three examples of power vegetables.

Correct Answer: Anything listed in the POW-R Health magazine.

Correct

No Yes

1) _____

2) _____

3) _____

CORRECT: Yes, that's right- good job! There are a lot of vegetables that are considered cruciferous vegetables.

INCORRECT: Ok, no problem, you missed *[state answers that are incorrect and correct]*. If you look at on page X of your POW-R Health Magazine, there is a list of cruciferous vegetables.

TB3.3 How many power vegetable servings do you need to eat each day.

Correct Answer: 1 serving/day

Correct

No Yes

CORRECT: Excellent, you're right. You only need to eat one power vegetable serving a day to help stop bladder cancer from coming back.

INCORRECT: Okay, no problem, the correct answer is 1 serving a day. You only need to eat one power vegetable serving a day to help stop bladder cancer from coming back.

TB4.3 What is the amount of 1 serving of a power vegetable?

Correct Answer: 1 cup at time of eating/consumption.

Correct

No Yes

CORRECT: Excellent, you're right. 1 serving of a power vegetable is 1 cup at the time you eat it. 1 cup is about the size of your fist.

INCORRECT: Okay, no problem, the correct answer is 1 serving of a power vegetable is 1 cup at the time you eat it. 1 cup is about the size of your fist.

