Thanks for taking the time to complete this call. Next week you will start receiving automated phone calls from our POW-R Health Program. The purpose of the calls will be to support you to eat more power vegetables. The calls will be tailored personally to you. Each call will ask you how many cups of power vegetables you ate for the week, figure out whether you are meeting your action plan goals, and then give you tailored support based on the obstacles and strategies you wrote down in your action plan. So, it will really be important for you to complete your POW-R Book every day, calculate your total power vegetables eaten at dinner or after dinner at the end of every week, and have that available when you receive the phone call.

The system will call you from this number: [name]. You can also call this number if you miss the call. This number is on the magnet we mailed to you to remind you that this is not a spam number. Can you please get the magnet we sent you out? Please place this magnet in a place that you'll be able to see it. If you miss a call, you can also call this number too to complete your automated phone call. There will be 11 automated phone call and we ask you to complete all 11 calls.

Each call will start by asking you what your date of birth is, so the system will know it is you. For example, if you were born January 3, 1953, you would enter 01-03-1953. The system will call you from this number: [name]. You can also call this number if you miss the call.

Can you tell me how you will enter your date of birth? *[Confirm that the participant can provide their DOB correctly]*

DOB

Correctly read

No

Yes

Each automated phone call will last about 10-15 minutes. Please stay on the phone until the call is complete, otherwise the system will think that you did not complete the call and it will call you again.

(Go over any magazine content questions they missed: Let's go over one last time the question(s) you missed)

What questions do you have for me before we hang up?

Okay, just remember, if you ever have any questions or concerns, you can always get a hold of us by calling one of our team members at [contact], [name]. This number is on the back of the Track Book and the last page of the magazine.

Record questions

Thank you for completing the call!

Control

Participant ID: _____

Staff Initials: _____

Date: _____

Start Time: _____

End Time: _____

Treatment Control

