Part G: Go over POW-R Track Book

One of the things you received in the packet we mailed to you is a POW-R Book. Please have your POW-R Book ready to review. In this book, I am asking that you keep track of how many fruit and vegetables you eat every day, and each week. Science shows that keeping track of what you eat is a powerful way to change your habits. Keeping track of how many fruit and vegetables you eat will help you eat more fruit and vegetables. Let's go over all of the parts of the POW-R Book.

Check box when section is covered

1. 1 POW-R book for each week; 24 sent to you—1 is for practice to use now; we are asking you to complete a track book each week for the entire program	3. 7 days in one POW-R book	5. Each day write down how many cups of fruit you had that day. (have them go through pages of book)	7. On the back is the phone number of the person from our team that you can call
---	-----------------------------	--	--

2. Cover page—write down dates of the week you are keeping track

4. Each day write down how many cups of vegetables you had that day. (have them open up book)

6. On the front page, is where you will write down: 1) the total cups of fruit, 2) total cups of vegetables, and 3) total number of fruits AND vegetables you ate that week. Place a check-mark by whether you ate at least 1.5 cups of fruit that week (yes/no). Same with vegetables. After our phone call, you will receive automated messages and will be asked to enter the total number of cups of fruit AND vegetables you ate for the week (refer them to last line). It will also ask you whether you ate at least 1.5 cups of fruit, and 2.5 cups of vegetables and you will use the information here to tell them 'yes' or 'no'

if you have any questions.

8. Any questions?

Let's practice using the POW-R Track Book.

Practice using POW-R Track Book

Take a POW-R Track Book. Can you think back this past week of any fruit you ate? Let's go through each day.

Now let's add how many cups you ate that week

	Monday	Tuesday	Wed	
	Thursday	Friday	Sat	Sunday
	Total			Correct
				No Yes

CORRECT: Yes, that's right- good job!

INCORRECT: Ok, so the correct total is X. Let's try that again to make sure you can use the POW-R Book correctly. Feel free to use a calculator if that would make things easier.

Part H: Going over magazine components: Teach Back Opportunity #3

Only ask questions that were answered incorrectly in Part E. SKIP if all questions were answered correctly in Part D or E.

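### The Track Book printed for the intervention arm in Appendix R has the control book's items and nowhere to record power vegetables

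*Combined protocol and SAP*

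**What the plan says.** Appendix R contains two Track Books, one under Intervention and one under Control. The front page of the Intervention book asks "How many fruits and vegetables did you eat this week" and "Did you eat at least 2.5 cups of vegetables this week", with a corresponding total and a 1.5-cup check for fruit. Each daily page asks for cups of vegetables and cups of fruit.

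Appendix Q, control script, Part G, describes that layout to control participants. One of its instructions is "Place a check-mark by whether you ate at least 1.5 cups of fruit that week", and the same is asked for vegetables.

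Appendix Q, intervention script, describes a different book:

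- Part G opens with "I am asking that you keep track of how many power vegetables you eat every day, and each week".
- On the daily entry it says "Only write down those power vegetables you ate at dinner or after dinner".
- On preparation it says "Each day you say whether you ate at least 1 power vegetable cup where you prepared it in a POW-R Health Preferred way".
- It also places a weekly power-vegetable total on the book's first page.
- The practice exercise asks "Can you think back this past week of any power vegetables you ate at dinner or after dinner".
- Part I tells participants what the automated system will want: "Each call will ask you how many cups of power vegetables you ate for the week".

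Sections 10 and 11 give, as likely components, booklets in which intervention participants log cruciferae daily and automated calls in which they key in the preceding week's servings. Section 11 (Participant Data and Sample Collection Procedures) cites Appendix R for the mailed track books.

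**The concern.** The two arms are meant to share delivery method and contact schedule but differ in content. Self-monitoring of cruciferae is part of the intervention content, and the weekly total in the book is what participants are told to have ready for each automated call. Section 11 (Personnel Training) also has staff use participant booklets to program the automated messages.

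A participant given the printed Intervention book would be tracking all vegetables and fruit. No cruciferae figure can be read off those entries. At stake are intervention fidelity and the contrast between arms.

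A related mismatch concerns what is counted. The script's book takes only power vegetables eaten at or after dinner. Sections 10 and 11 describe daily cruciferae intake and prior-week servings with no time-of-day limit. Part I of the script gives both versions: the call asks for the week's cups, while the participant is told to total the dinner-or-later cups.

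**Working it through.** This is a comparison of texts; no power or alpha figure is involved.

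**Step 1. Count the items in the Intervention book (Appendix R), leaving out the week's dates.**

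- Daily: 7 days × 2 items (vegetables, fruit) = 14.
- Weekly: fruits and vegetables this week; total vegetables; 2.5-cup vegetable check; total fruit; 1.5-cup fruit check = 5.
- Total: 14 + 5 = 19.

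**Step 2. Compare with the Control book (Appendix R).** It has the same 14 daily and 5 weekly items, so 19 of 19 are shared. None of the 19 names power or cruciferous vegetables, dinner or preparation.

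**Step 3. Compare with the two call scripts (Appendix Q).**

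| Script, Part G | Fields described | Found in the Intervention book |
|---|---|---|
| Control | daily vegetables; daily fruit; weekly fruit total; weekly vegetable total; weekly combined total; fruit check; vegetable check (7) | 7 of 7 |
| Intervention | daily cups of power vegetables at or after dinner; daily preparation item; weekly power-vegetable total (3) | 0 of 3 |

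The book headed Intervention is therefore the one that control staff are told to explain.

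**Step 4. Look for the right book elsewhere.** Section 11 (Intervention Design) refers to Appendix P for the mailed materials, including the booklets. Appendix P prints only the two magazines. No power-vegetable book appears in the text available for this review.

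**Step 5. Rule out a reading fault.** Both books can be read in full, all seven days each, and nothing in Appendix R is marked as missing. A lost page is an unlikely explanation. The likeliest one is that the control book was filed twice.

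**The case against.** The strongest reply concerns weight, since the mismatch with the script is not in dispute. If the control book was simply filed twice, this is an appendix-assembly error with no demonstrated consequence. The intervention magazine, the action plan and Table 1 all point at the right target. Part G has staff and participant open the book together and practise a weekly total, so a wrong book would probably be noticed on the first completed call. The provision for participants who had finished follow-up by the March 2022 revision suggests that calls may already have been run. The primary outcomes come from the cruciferae questionnaire and the urine assay (section 8), not from the Track Book.

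Much of this stands, and it is why no effect on message routing, outcomes or power is claimed. It does not make the printed page harmless. Appendix R is the document cited for mailing, and the intervention script lists 24 copies of the book among the materials sent before the live call. Discovery on that call would come after the mailing.

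Two narrower points have some force:

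- Sections 10 and 11 describe the components as likely and open to change during adaptation. The firm contradiction is with the Appendix Q script, and it does not depend on those sections.
- Recording every day and recording only the evening portion are compatible instructions, and evening eating is the plan's stated strategy. The dinner point therefore rests on the difference from the untimed servings in sections 10 and 11 and on the two versions in Part I. It is secondary to the main finding.

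It could also be said that section 11 introduces Appendix R in general terms covering fruit and/or vegetables. That wording serves both arms and does not supply the three fields that the script goes through.

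**Conclusion.** The concern holds and should be fixed. The Intervention Track Book shares 19 of 19 items with the control book, matches 7 of 7 control-script fields and matches 0 of 3 intervention-script fields. As printed, it cannot supply the weekly power-vegetable total that the automated call requests.

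The planned intervention arm is 40 participants. How many received this book is not stated and may be none. The conclusion is that the appendix contradicts the intervention script and differs from the components in sections 10 and 11. It assumes nothing about what was mailed, and no bias in the primary comparison can be derived from the documents.

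One minor slip goes with it. The control script keeps power-vegetable wording in two places: the response for participants who have reviewed the packet (A2) and the eating-goals heading in Part F.

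**What to change.** 1. Replace the Intervention pages of Appendix R with a power-vegetable book whose fields match the intervention script: daily cups, the preparation item and the weekly total used for the call.
2. In the same amendment, reconcile the script's dinner-or-later count with the daily intake and prior-week servings in sections 10 and 11, so that the book, script and automated call count the same thing. Which count to use is for the study team to decide.
3. Correct the Appendix P reference in section 11 (Intervention Design) so that it leads to the booklets.
4. Check mailing records, or whatever evidence exists, for which book was sent. If the wrong one went out, report it as a fidelity deviation with the number of participants affected.
5. Change the leftover power-vegetable wording in the control script to fruit and vegetables.

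The cost is corrected pages, a minor amendment and a records check. A reprint is needed only if the wrong book is in use.

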Appendix S. Participant Thank You Letter

[DATE]

[FIRST AND LAST NAME OF PARTICIPANT]

[STREET ADDRESS]

[figure not shown]
[CITY, STATE ZIP CODE]

Dear [FIRST NAME OF PARTICIPANT],

I am writing to thank you personally for completing the [baseline/follow-up] assessment of the POW-R Health Program. To show our appreciation for your time and effort, we have enclosed Tops gift card for \$X. In 6 months, we will ask you to complete these surveys again and if you do, you will earn another \$X.

On behalf of the POW-R Health team, thank you so much for supporting our research! Please don't hesitate to contact us at: [contact], [name].

Sincerely,

[name]
Principal Investigator

[name]
Principal Investigator

Appendix T. Recruitment Letter for Roswell Park Cancer Registry

Date

Dear Participant,

We recently received funding from the National Institutes of Health to learn more about how diet may reduce the risk of recurrence in individuals with early-stage bladder cancer. Men and women who were recently diagnosed with early-stage bladder cancer and who live in the counties of Niagara, Orleans, Genesee, Erie, Wyoming, Chautauqua, Cattaraugus, and Allegany may be eligible for the study.

We are asking you to take part in this study because you have been diagnosed and treated for bladder cancer. The goal of this study is to make a healthy eating program to improve cancer outcomes. The purpose of this study is to compare two types of healthy eating programs. This study will allow the researchers to know whether different types of healthy eating programs can improve the bladder cancer outcomes of the patients. The intervention that you will receive as part of this study will be given to you at no cost.

If you agree to take part in this research study, you will receive a \$100 gift card for completion of the baseline surveys and you will receive another \$100 gift card for completion of the 6-month survey.

This study has been reviewed and approved by the Roswell Park Institutional Review Board to assure that the study plans will not put any participants at risk. Your involvement in this study does not involve any physical risk to you. The possible risks might be feeling uncomfortable answering questions, embarrassment, or someone identifying you as a participant in the group, although this would be rare. You will not receive any direct health benefit from participating in this study.

Someone from our office will call you to make sure you received this letter and to discuss the study with you. If you have any questions, please call us at [name]. We hope that you will be able to help us by completing the survey.

We hope to hear from you soon!

